1.2 RATIONALE FOR THE STUDY AND STUDY DESIGN

1.2.1 *Rationale for the study*

Sabin 2 vaccine component has been withdrawn from routine use globally from April 2016 per the current SAGE recommendations. Following this OPV2 cessation, stockpiles of mOPV2 will be maintained for potential use in outbreak response. However, there is a risk of cVDPV2 from Sabin type 2 in settings of low population immunity. Research has been ongoing to develop vaccines that are genetically more stable than the currently available Sabin 2 containing OPVs.

Two nOPV2 vaccine candidates have been developed as attenuated serotype 2 polioviruses derived from a modified Sabin 2 infectious cDNA clone. nOPV2 Candidate 1 (S2/cre5/S15domV/rec1/hifi3) and nOPV2 Candidate 2 (S2/S15domV/CpG40) were generated by modifying the Sabin-2 RNA sequence to improve phenotypic stability and make the strains less prone to reversion to virulence. The two nOPV2 candidate vaccine strains have been used as an investigational medicinal product (IMP) in a first-in-human (FIH) Phase 1 containment trial in 2 groups of 15 healthy IPV-only vaccinated adults in Belgium, to evaluate the general safety and immunogenicity of both of the nOPV2 candidate vaccine strains (EudraCT number 2017-000908-21, ClinicalTrials.gov: NCT03430349).

Preliminary data from the study have been evaluated. Most of the volunteers in the study were men (25 of the 30), and the average age was 32.8 years (ranging from 21 to 50 years of age). The two groups of volunteers were similar in terms of the number of men and women and their age. Most of the volunteers had five or six vaccinations with IPV in the past. All volunteers completed the study.

In general, the two vaccine candidates were well tolerated. There were no serious adverse events reported, and no severe illnesses thought to be due to the vaccine candidates. Most health events reported during the study were generally mild, and all resolved.

Some volunteers in both groups had abnormal blood tests. None of the volunteers experienced symptoms associated with these laboratory test changes, and it is not clear whether these were due to vaccine or due to other causes, such as intense exercise (during the weeks of being restricted to the research facility, volunteers had exclusive access to a gym in the study facility). The next study will include blood tests to look into this further.

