Blood tests to assess whether the vaccine candidates resulted in the desired protective response to poliovirus were encouraging. Volunteers demonstrated clear immune response to both vaccine candidates.

The stool samples of most of the volunteers tested positive for the vaccine candidates. These observations were anticipated based on experience with Sabin OPV2 from which

these candidates were derived. Presence of vaccine virus was observed somewhat more for vaccine candidate #1 than #2. Some volunteers had more prolonged shedding of vaccine virus in stool, with the longest period for vaccine candidate #1 being almost 3 months and for vaccine candidate #2 just over a month-and-a-half (more detailed data are reported in the IB). None of the volunteers demonstrated any illness associated with longer duration of shedding of vaccine virus.

As an exploratory analysis, samples from subjects that shed the candidate vaccines in stools were tested for neurovirulence as well as by deep sequencing. Data collected to date support the phenotypic stability (lack of significant reversion) of the nOPV2 candidates. No meaningful increases in neurovirulence could be detected and sequencing confirmed that there were no reverting mutations in the main site of attenuation which are analogous to the domain V A481G reversion in Sabin OPV2.

1.2.2 *Rationale for the study design*

1.2.2.1 *OVERALL STUDY DESIGN*

Due to the withdrawal of Sabin mOPV2 and prohibition of its use from April 2016 onwards, well before the availability of nOPV2 for clinical testing, Phase 4 trials have been conducted with Sabin mOPV2 to provide control data on safety, immunogenicity, against which data for nOPV2 in subsequent Phase I and II studies will be evaluated and compared. The Phase 4 trials of Sabin mOPV2 were designed to parallel the expected design of the Phase 1 and 2 nOPV2 studies with respect to overall design, inclusion of similar study cohorts. As for these reasons head to head comparison of nOPV2 and mOPV2 is not possible, the overall clinical development plan with the Phase I and II studies was designed taking into consideration the unique situation of OPV2 cessation in April 2016, and the global public health need of a vaccine with lower risk of VAPP and VDPV for outbreak response in the post-cessation era.

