The potential risks posed by transmission of the nOPV2 candidate vaccine strains or their genetic variants to an unintended human recipient are estimated by combining the likelihood of transmission with the magnitude of the consequences if transmission occurs. For the groups in which transmission is most likely to occur (close contacts of the study subjects and study site personnel), these consequences are negligible due to previous vaccination, therefore also the overall risk is negligible. The likelihood of transmission to other unintended recipients is considered to be negligible for the general population and low for those in close contact with family members of the study participants. As polio vaccination has been mandatory in Belgium since 1966 and the rate of vaccination of the inhabitants is >95%, practically the entire population is effectively protected from disease caused by the poliovirus, including VAPP. Therefore, the magnitude of the consequences of the nOPV2 candidate vaccine strains or their genetic variants is considered negligible for this group although for those who are unvaccinated or immunocompromised consequences of low magnitude are expected (taking into account the extremely low frequency of occurrence of the serious adverse event of VAPP).

Preliminary data obtained with the candidate nOPV2 vaccines in a first-in-human Phase 1 clinical study in Belgium with IPV-only vaccinated adults (>18 years old) (EudraCT number 2017-000908-21, ClinicalTrials.gov: NCT03430349), confirm that in IPV primed subjects, fecal shedding occurs following administration of the nOPV2 candidate vaccines, with median durations of fecal shedding of about 2 and 4 weeks for the two candidates, yet no nasopharyngeal shedding was observed in this study. This is generally in line with expectations for individuals with an IPV-only vaccination history who are given Sabin OPV.

Presence of vaccine virus in stool was observed somewhat more for vaccine candidate #1 than #2. Some volunteers had more prolonged shedding of vaccine virus in stool, with the longest period for vaccine candidate #1 being almost 3 months and for vaccine candidate #2 just over a month-and-a-half (more detailed data are reported in the IB). None of the volunteers demonstrated any illness associated with longer duration of shedding of vaccine virus.

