4. STUDY DESIGN

4.1 OVERVIEW OF STUDY DESIGN

This will be a multicenter, partial blind, placebo-controlled, randomized study in 200 healthy OPV-vaccinated adults and **in 48 to 132** healthy IPV-only vaccinated adults (18 to 50 years), as follows:

- 50 OPV-vaccinated adults to receive 1 dose of nOPV2 candidate 1 (Group 1);
- 50 OPV-vaccinated adults to receive 2 doses of nOPV2 candidate 1 (Group 2), administered 28 days apart;
- 50 OPV-vaccinated adults to receive 1 dose of nOPV2 candidate 2 (Group 3);
- 50 OPV-vaccinated adults to receive 2 doses of nOPV2 candidate 2 (Group 4), administered 28 days apart;
- **16 to 44** IPV-only vaccinated adults to receive 2 doses of nOPV2 candidate 1 (Group 5), administered 28 days apart;
- **16 to 44** IPV-only vaccinated adults to receive 2 doses of nOPV2 candidate 2 (Group 6), administered 28 days apart.
- **16 to 44** IPV-only vaccinated adults to receive 2 doses of placebo (Group 7), administered 28 days apart.

Groups will be enrolled sequentially such that subjects receiving candidate 2 will be enrolled first (IPV and OPV groups simultaneously), followed by subjects receiving candidate 1. IPV-only vaccinated adults will be randomized 2:1 to candidate 2 (Group 6) or placebo (Group 7), respectively, until all **16 to 44** Group 6 subjects are enrolled, after which randomization 2:1 to candidate 1 or placebo will commence for Groups 5 and 7. For OPV-vaccinated subjects, randomization to Groups 1 and 2 to receive candidate 1 will ensue following complete randomized enrollment of subjects to Groups 3 and 4. In all cases, block randomization will be used to ensure balanced randomization across time.

The DSMB has established stopping rules for safety prior to study start which will be continuously assessed. **The DSMB will also monitor study enrollment, particularly for IPV-vaccinated subjects, and recommend truncation and/or closure of study groups if enrollment stagnates and when current enrollment is considered sufficient to meet study objectives and no safety signals occurred.** The minimum number of IPV-vaccinated subjects agreed on by DSMB per vaccine candidate is 24. With a randomization of 2:1 for placebo the minimum study cohort size for Groups 5, 6 and 7 will be 16. In case of safety signals the DSMB reserves the right to reverse the truncated enrollment.

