8.2 IMMUNOGENICITY

8.2.1 *Immunogenicity Variables*

Neutralizing Type 2 Poliovirus Antibody Titers

Blood samples for the determination of neutralizing type 2 poliovirus antibodies will be taken at the time points specified in the Time and Events schedule.

Neutralizing antibodies against type 2 poliovirus will be determined using a sero-neutralization assay.

Detailed descriptions of the collection, handling, transport and processing of the blood samples will be included in the laboratory manual.

Viral Shedding

Stool samples will be collected at the time points outlined in the Time and Events schedule.

As a measure of intestinal immunity, shedding of type 2 poliovirus in the stools will be evaluated using:

- Quantitative PCR (viral identity).
- CCID₅₀ determination (titer).

The shedding analyses will initially be conducted using a subset of samples in the 10 days following administration of each dose (e.g. day 0, 3, 7, and 10) and all samples at day 14 and thereafter. The remaining samples will be stored pending evaluation of the initial analyses; PCR and CCID₅₀ will be conducted on these stored samples if deemed important for the complete interpretation of the study results.

Shedding results for last stool sample will be provided to the sites in a timely manner in order to inform subjects about the need for further stool sampling every 3 weeks and taking precautions.

Detailed descriptions of the collection, handling, transport and processing of the stool samples will be included in the laboratory manual.

8.2.2 *Immunogenicity Criteria*

For an overview of endpoints, see Section 3.

The following endpoints will be based on neutralizing type 2 poliovirus antibody titers:

- Seroprotection: poliovirus type 2-specific titers $\geq 1:8$;
- Seroconversion: a change from seronegative to seropositive and antibody titers of $\geq 1:8$, and in seropositive subjects, as an antibody titer increase of ≥ 4 fold over baseline titers;
- Median titer and GMT 28 days post-vaccination and 56 days post-vaccination for Groups 2, 4, 5 and 6.

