6.7.1 Exploratory Viral Shedding Endpoints

Throughout, viral shedding analyses will be conducted by group and dose number. The descriptive summaries below will also be computed separately by site. Between-group inferential analyses will additionally be conducted among the site in common between UAM1 and UAM4, for OPV-vaccinated subjects, if the post-dose-1 between-site GMT comparison indicates a significant difference in immunogenicity between sites. The shedding analyses will be conducted considering all available samples, collected at Days 0-10, 14, 21, 28, and 42 following each dose (with day of vaccination defined as Day 0) and additional samples collected, as necessary, to define the end of shedding for participants. All viral shedding data will be listed, including both sample collection and assay results.

Categorical summaries of type 2 viral shedding positivity (positive via PCR) and continuous summaries of viral titers (\log_{10} CCID₅₀/g among both shedders and shedders/non-shedders combined) will be produced by group and by post-vaccination day. Each of these will be augmented with two-sided 95% confidence intervals. The Clopper-Pearson exact method will be used for shedding positivity rate, and the bootstrap method (10,000 replicates, quantile method) will be used for the median \log_{10} viral titers. Subjects who are PCR-negative for viral shedding at a given time point will be assigned the value of 0 for computations involving the \log_{10} CCID₅₀/g, and values PCR positive for type 2 poliovirus but below LLOQ ($2.75 \log_{10}$ CCID₅₀/g) or above ULOQ ($8.25 \log_{10}$ CCID₅₀/g) will be assigned the corresponding value of LLOQ or ULOQ.

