For each subject, the extent of viral shedding will be calculated as the area under the curve (using the linear trapezoidal method) of \log_{10} -transformed values of viral concentration in stool samples as determined using quantitative PCR (viral identity) and CCID₅₀ (titer) from samples taken through 28 days following each vaccine dose, and this continuous variable will be summarized. If a subject is missing two consecutive shedding data points among those intended to be tested for this computation due to samples not provided and/or unevaluable samples, the subject will have a missing value. This requirement regarding consecutive missing samples may be relaxed at the analysis stage if sample size for this computation is significantly impacted. Additionally, the Sheding Index Endpoint (SIE) will be computed as the arithmetic mean of \log_{10} CCID₅₀/g obtained from Days 7, 14, 21, and 28. Here, a single missing daily value will lead to a missing

SIE value, although windows of +/- 2 days will be applied to sample availability. If samples are available at both +1 (+2) and -1 (-2), then the mean \log_{10} CCID₅₀/g from these two days will be used for this computation. This will be summarized as a continuous variable using the same methods for daily viral shedding described above.

Additionally, a summary of time-to-shedding-cessation will be prepared using Kaplan-Meier methods. The day of cessation of shedding will be defined as the day of the first sample negative for shedding after which the following two samples are also negative. Summaries will be produced using Kaplan-Meier methods, and will include quartiles and corresponding 95% confidence intervals, as well as the estimated shedding rate at study days 3, 5, 7, 10, 14, 21, and 28 with corresponding 95% confidence intervals. Subjects who are positive for type 2 viral shedding at their last available assessment date with an evaluable stool sample, or who fail to cease shedding prior to a 2nd dose will be right-censored at the last time point they were known to be shedding virus. The time-to-shedding-cessation curves will be displayed graphically, and the comparison of the difference in time to shedding cessation curves between candidate groups in study M4 and corresponding controls subjects from study UAM1 will be conducted by computing the two-sided log-rank p-value.

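### SAP 6.7.1 censors dose-1 shedding at dose 2 but has no matching rule after dose 2, so residual dose-1 virus enters every post-dose-2 shedding summary

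*SAP*

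**What the plan says.** Groups 2, 4, 5 and 6 receive the same candidate twice, 28 days apart (Protocol 4.1; for Group 5, "IPV-only vaccinated adults to receive 2 doses of nOPV2 candidate 1 (Group 5), administered 28 days apart").

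SAP 6.7.1 sets the general rule: "Throughout, viral shedding analyses will be conducted by group and dose number". It numbers stool days from each dose, with the vaccination day as Day 0. The area under the curve is computed "from samples taken through 28 days following each vaccine dose, and this continuous variable will be summarized". The shedding index averages Days 7, 14, 21 and 28, and SAP 3.5.3 asks for time to cessation after each dose. SAP 6.7 uses the per-protocol population after dose 2; neither SAP 4.3 nor Protocol 5.3 contains a criterion on shedding status at dose 2.

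The one rule on overlap is in SAP 6.7.1: a subject who has not stopped shedding before dose 2 is right-censored at the last time known to be shedding. This protects the dose-1 curve only.

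Protocol 1.3.1 reports Phase 1 results in IPV-only adults "with median durations of fecal shedding of about 2 and 4 weeks for the two candidates". Protocol 8.2.1 introduces the stool assays with "As a measure of intestinal immunity, shedding of type 2 poliovirus in the stools will be evaluated using". Appendix 4 says the PCR tells each candidate from the other and from Sabin OPV2.

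**The concern.** One continuous shedding episode that spans Day 28 is treated in two ways. In the dose-1 analysis it is censored. Its remainder is then counted from a new Day 0 as shedding after dose 2. The assay cannot correct this, because it separates strains and not doses.

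The direction is predictable. Carry-over raises post-dose-2 positivity, titre, area under the curve, shedding index and duration, and more so for the candidate that sheds longer. A natural use of a second dose is to ask whether the first reduced later shedding. Since the protocol treats shedding as a measure of intestinal immunity, carry-over would make that reduction look smaller than it is.

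**Working it through.** The Phase 1 medians are observed results. The documents hold no subject-level data, so the medians cannot be reproduced. The check asks what they imply at Day 28 and later.

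**Inputs**
- Dose interval: 28 days (Protocol 4.1).
- Median shedding: about 14 and 28 days (Protocol 1.3.1), from "2 groups of 15 healthy IPV-only vaccinated adults in Belgium" (Protocol 1.2.1). The sentence does not assign the medians to candidates. The longer one is probably candidate 1, since "Presence of vaccine virus in stool was observed somewhat more for vaccine candidate #1 than #2".
- Longest durations: "with the longest period for vaccine candidate #1 being almost 3 months and for vaccine candidate #2 just over a month-and-a-half" (Protocol 1.2.1).
- IPV group size: 16 to 44 (Protocol 4.1).

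**Formula.** Share still shedding t days after dose 1: S(t) = 0.5^((t/median)^k). The shape k is an assumption. I use k = 1 (exponential) and k = 2 (steeper) as the range. Setting the tail to 1/16 at the reported maxima, taken as about 85 and 47 days, gives k of about 1.25 and 1.14, inside that range.

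**Share at dose 2 (t = 28)**
- 28-day median: 0.5^1 = 50% for any shape, that is 8 of 16 to 22 of 44.
- 14-day median: 0.5^(2^2) = 6% to 0.5^2 = 25%, that is 1 to 4 of 16, or about 3 to 11 of 44. The fitted shape 1.14 gives 22%.

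**Positivity after dose 2 if dose 2 produced no shedding at all** (k = 2 to k = 1)

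| Day after dose 2 | t | 28-day median | 14-day median |
|---|---|---|---|
| 0 | 28 | 50% | 6–25% |
| 7 | 35 | 34–42% | 1–18% |
| 14 | 42 | 21–35% | 0–13% |
| 28 | 56 | 6–25% | 0–6% |

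For example, at Day 7 with the 28-day median: 0.5^(35/28) = 42% and 0.5^((35/28)^2) = 34%.

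**Mixed with true dose-2 shedding.** If 20% were positive at Day 7 because of dose 2 (assumed, and independent of carry-over c), the table would show 1 − 0.8 × (1 − c). With c = 34 to 42% this is 47 to 54%. With c = 1 to 18% it is 21 to 34%.

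**Shedding index.** SAP 6.7.1 gives a PCR-negative stool the value 0 and a positive stool at least 2.75 log10. One residual positive at Day 7 alone therefore adds at least 2.75/4 = 0.69 to that subject's index.

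**Precision of the 50%.** If the median is 24 to 32 days, S(28) runs from 39% to 59% over k = 1 to 2. With 15 subjects, about 7 or 8 would lie beyond the median; exact 95% limits are 21–73% for 7/15 and 27–79% for 8/15.

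**The case against.** Several points on the other side stand.

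- **Attribution.** A reader might infer that the SAP treats post-dose-2 shedding as caused by dose 2. It does not say so. It organises tables by dose, and SAP 6.7 calls the analyses descriptive while adding tests against UAM1. Total virus shed after a second dose is also a legitimate quantity for a live vaccine.
- **Visibility.** Carry-over is not hidden. SAP 6.7.1 tabulates positivity by group and day, and the two-dose schedule (Protocol 8.1) marks the Day 28 stool as taken before vaccination. The post-dose-2 Day 0 row thus largely shows the share positive at dose 2, with UAM1 alongside for OPV groups (SAP 5.1). A separate request for that percentage would be nearly redundant.
- **UAM1 contrasts.** A reader might infer that these are distorted. The medians come from IPV-only adults, whereas the contrasts are in OPV-vaccinated adults (SAP 6.7.1), for whom the documents give no shedding duration. UAM1 Group 2 also had dose 2 at Day 28, so carry-over may exist in both arms; it cancels only if persistence is equal. SAP 6.7.2 reports only 2 post-dose-1 UAM1 samples suitable for the neurovirulence assay. That hints at little high-titre shedding but does not measure PCR persistence.
- **Size.** Not having ceased is not the same as being positive on the day, because cessation needs three consecutive negatives. Protocol 1.2.1 says that most volunteers, not all, had positive stools, and the denominator of the medians is not given. Fifty per cent may be too high.
- **Selection.** It is tempting to rest conclusions on subjects negative before dose 2. They are early clearers or subjects in whom dose 1 did not take. Restricting to them conditions on an outcome of vaccination, and the selection may differ between candidate and Sabin.

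None of this supplies the missing rule. The by-day table shows how many subjects are affected; it does not show what the post-dose-2 area under the curve, index or cessation curve would be without them.

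**Conclusion.** The gap is real and narrow. As written, residual dose-1 virus counts in all post-dose-2 shedding summaries. In the IPV groups it could concern roughly half of one candidate's subjects at dose 2 and perhaps 6 to 25% of the other's. The first figure rests on an approximate median from 15 people; the second also on assumed curve shapes. In the OPV groups the size is unknown, so a bias in the UAM1 contrasts is possible but not shown. IPV shedding has no historical comparison. All the endpoints are exploratory, and no primary or secondary result changes. No view is taken on the dose interval.

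**What to change.** In SAP 6.7.1, add a sensitivity analysis:

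1. Repeat the post-dose-2 summaries (daily positivity, titre, area under the curve, shedding index, time to cessation) and the UAM1 Group 2 contrasts by PCR status, negative or positive, in the last evaluable stool before dose 2. Show them next to the all-subject version.
2. State how subjects positive at dose 2 enter the post-dose-2 Kaplan-Meier analysis.
3. Note that the PCR-negative subset is smaller and selected for early cessation or no take, so neither version alone should support conclusions about dose-2 shedding or intestinal immunity.

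The samples are already planned: the stool one or two days before Visit 4 in both studies, and the pre-vaccination Day 28 stool in this one. The cost is SAP wording and a second set of tables. The limit is size: with a 50% carry-over share, a group of 16 leaves about 8 PCR-negative subjects and a group of 44 about 22.
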